3.5.2 Handling of missing data for the primary endpoint

As this is a retrospective, non-interventional study, information may not be systematically collected at each time-point of interest, resulting in missing data.

All patients in the efficacy population without a missing response will be used for the primary analysis of the primary endpoint (complete case analysis).

The completeness of the response variable will be enumerated by reporting the following:

- Reasons for missing response at week 24 or 6 months (+/- 4 weeks), including missing imaging scans, as available (e.g., insurance considerations, age considerations, absence of overgrowth, differences in clinical practice) where available will be reported.
- Differences in the patient population with regard to demographic and clinical characteristics (e.g., age, PROS sub-type) will be reported in a table for patients with and without 24 weeks or 6 months (+/- 4 weeks) assessments.

For the primary endpoint, 1 to 3 target lesions identified at index date via central review of imaging scans are considered. If information about volumetric assessment of one or two identified target lesions at index date is missing/non-evaluable at Week 24 time point (24 weeks or 6 months (+/- 4 weeks)), the sum of target lesions volume will be calculated using only the target lesion with paired assessment available.

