### Definition of response

Patients included in the analysis population for the primary endpoint will be defined as responders if they meet all of the following criteria:

- Patient achieved  $\geq 20\%$  reduction from index date (or up to 12 weeks prior) in the sum of target lesion volumes (1 to 3 lesions, via central radiological assessment) by the change between the index date and 24 weeks (+/- 4 weeks) following the index date
- None of the individual target lesions has  $\geq 20\%$  increase from index date to Week 24 (+/- 4 weeks)
- Patient did not permanently discontinue alpelisib prior to 24 weeks of treatment
- Patient did not require surgery as rescue therapy between index date and 24 weeks of treatment with alpelisib due to disease deterioration.
- No progression of non-target lesions at Week 24 (+/- 4 weeks)
- No appearance of new lesion at Week 24 (+/- 4 weeks)

Patients will be considered as having a missing response if volume assessment at 24 weeks (+/- 4 weeks) following the index date was not performed and:

- Patient did not permanently discontinue alpelisib prior to 24 weeks of treatment
- Patient did not require surgery as rescue therapy between index date and 24 weeks of treatment with alpelisib due to disease deterioration.

Patients will be defined as non-responders in all other cases. In particular, patients with MRI scan performed at Week 24 (+/- 4 weeks) for which the volumetric measurement of the selected target lesions (1 to 3 lesions, via central radiological assessment) cannot be calculated will be considered as non-responders.

Disease progression at any assessment is defined as an increase of any individual target lesions of  $\geq 20\%$  in volume from previous assessment, progression of non-target PROS lesions or appearance of a new PROS lesion.

Relative to non-target lesions, progression will be assessed for the lesions that are identified at index date (or up to 12 weeks prior) with available information at Week 24 (+/- 4 weeks) and new lesions. At Week 24 the central imaging reviewer will make a conclusion if overall level of non-target disease burden decreased or increased unequivocally.

All patients in the efficacy population without a missing response will be used for the primary analysis of the primary endpoint (complete case analysis).

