3.5.1 Definition of response

Patients included in the analysis population for the primary endpoint will be defined as responders if they meet the following criterion:

- Patient achieved $\geq 20\%$ reduction from index date (or up to 24 weeks prior) in the sum of target lesion volumes (1 to 3 lesions, via central radiological assessment) by the change between the index date and 24 weeks or 6 months (+/- 4 weeks) following the index date
- None of the individual target lesions has $\geq 20\%$ increase from index date to Week 24 or 6 months (+/- 4 weeks)
- Patient did not permanently discontinue alpelisib prior to 24 weeks of treatment

- Patient did not require surgery as rescue therapy between index date and 24 weeks of treatment with alpelisib due to disease deterioration
- No progression of non-target lesions at Week 24 or 6 months (+/- 4 weeks)
- No appearance of new lesions at Week 24 or 6 months (+/- 4 weeks)

Patients will be defined as non-responders if they meet at least one of the following criteria:

- Patient achieved < 20% reduction from index date (or up to 24 weeks prior) in the sum of target lesion volumes (1 to 3 lesions, via central radiological assessment) by the change between the index date and 24 weeks or 6 months (+/- 4 weeks) following the index date
- Any of the individual target lesions has $\geq 20\%$ increase from index date to Week 24 or 6 months (+/- 4 weeks)
- Patient permanently discontinued alpelisib prior to 24 weeks of treatment
- Patient require surgery as rescue therapy between index date and 24 weeks of treatment with alpelisib due to disease deterioration.
- Progression of non-target lesions at week 24 or 6 months (+/- 4 weeks)
- Appearance of new lesion at week 24 or 6 months (+/- 4 weeks)
- Patients with MRI scan performed at week 24 or 6 months (+/- 4 weeks) for which the volumetric measurement of the selected target lesions (1 to 3 lesions, via central radiological assessment) cannot be calculated.

Patients will be considered as having a missing response if lesion volume(s) assessment at 24 weeks or 6 months (+/- 4 weeks) following the index date is not available and:

- Patient did not permanently discontinue alpelisib prior to 24 weeks of treatment and
- Patient did not require surgery as rescue therapy between index date and 24 weeks of treatment with alpelisib due to disease deterioration.

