All patients in the efficacy population without a missing response will be used for the primary analysis of the primary endpoint (complete case analysis).

Surgery as rescue therapy is considered as required due to worsening of any existing lesions or development of a new lesions requiring intervention while on alpelisib treatment.

Disease progression at any assessment is defined as an increase of any individual target lesions of $\geq 20\%$ in volume from previous assessment, progression of non-target PROS lesions or appearance of a new PROS lesion.

Progression based on non-target and new lesions will be based on radiological assessment of the central reader.

In relation to non-target lesions, progression will be assessed for the lesions that are identified at index date (or up to 24 weeks prior) with available information at Week 24 or 6 months (+/- 4 weeks) and new lesions. At Week 24 the central imaging reviewer will make a conclusion if overall level of non-target disease burden decreased or increased unequivocally.

Evaluation of radiographic response and progression of all measurable lesions (target and non-target) will be provide to Novartis by a third party vendor. All details are summarized in the Independent Central Review Charter (ICRC).

Table 3-3 Primary endpoint measure

Measure	Type of variable	Statistics	Time point for reporting
Proportion of patients with response at Week 24 provided that none of the individual target lesions have $\geq 20\%$ increase from index date and in absence of progression of non-target lesions and without new lesions	Binary	n, missing, frequency, percentage, 95% CI	At 24 weeks (6 months)

The primary analysis for this study will be descriptive in nature (estimation based), and therefore no hypothesis testing will be conducted. Categorical and binary data will be presented by frequency counts and percentages. The Clopper-Pearson exact method will be used to estimate 95% CIs for binary data.

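### SAP 3.5.2 lets response be judged when one or two selected target lesions went unmeasured at Week 24, and does not say how the individual-lesion growth criterion is then met

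*SAP*

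**What the plan says.** Four rules bear on a patient with some, but not all, selected target lesions measured at Week 24.

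- **Partial measurement (SAP 3.5.2).** The trigger is "If information about volumetric assessment of one or two identified target lesions at index date is missing/non-evaluable at Week 24 time point". The consequence is that "the sum of target lesions volume will be calculated using only the target lesion with paired assessment available".
- **Growth criterion (SAP 3.5.1).** Besides the 20% fall in the sum, a responder must satisfy a condition that begins "None of the individual target lesions has" and sets the limit at an increase of 20% or more. It applies lesion by lesion.
- **Unmeasurable scan (SAP 3.5.1).** A patient is a non-responder if a Week 24 MRI was done "for which the volumetric measurement of the selected target lesions (1 to 3 lesions, via central radiological assessment) cannot be calculated". Protocol 6.8.1 has the same rule: patients whose volume "cannot be calculated will be considered as non-responders".
- **Missing response.** In SAP 3.5.1, response is missing if "lesion volume(s) assessment at 24 weeks or 6 months (+/- 4 weeks) following the index date is not available" and there was neither early discontinuation nor rescue surgery. The protocol's condition is that the "volume assessment at 24 weeks (+/- 4 weeks) following the index date was not performed".

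The protocol has no paired-lesion rule for target lesions; section 6.9 gives one for non-target lesions only. SAP section 2, on changes to the protocol analysis, lists time windows and nothing else. Both sensitivity analyses in SAP 3.5.3 (multiple imputation, and best and worst case) are confined to patients with missing response.

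**The concern.** The primary endpoint is composite: the sum must fall, and no single target lesion may grow materially. SAP 3.5.2 repairs the first part when lesions are unmeasured and is silent on the second. A lesion without a Week 24 volume cannot show disqualifying growth. If the program simply checks the observed lesions, the criterion passes by default.

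The classification is also unsettled. With one lesion measured and two non-evaluable on the same MRI, one programmer could follow 3.5.2 and call a response, and another could follow the non-responder rule in 3.5.1. Both would be reading the SAP in good faith. The rate at stake is the headline result of a single-arm study whose results, under protocol section 9, are intended for health authorities.

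**Working it through.** **1. The plan's own figures.** Protocol 6.6 takes 50 patients for precision. Clopper-Pearson 95% limits for x = 10, 15, 20 and 25 of 50 are 0.100–0.337, 0.179–0.446, 0.264–0.548 and 0.355–0.645. All match Table 6-2 to three decimals, and the widths agree within 0.001. The point below does not affect that table, but n = 50 is the base for sizing it.

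**2. The rules side by side.** Take a patient with no early discontinuation, no rescue surgery, no new lesion and no non-target progression.

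| Week 24 target-lesion data | SAP 3.5.2 | SAP 3.5.1, MRI rule read as *any* lesion | SAP 3.5.1, MRI rule read as *all* lesions |
|---|---|---|---|
| All measured | not triggered | judged on all | judged on all |
| Some measured, the rest non-evaluable on MRI | judged on paired lesions | non-responder | not triggered, so 3.5.2 applies |
| Some measured, the rest not imaged | judged on paired lesions | does not clearly apply | does not apply |
| MRI done, none calculable | no paired lesion to use | non-responder | non-responder |

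The second row is where the rules collide or coexist, depending on one unstated word. The growth criterion is unaddressed in both middle rows.

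**3. What partial measurement does to one patient.** The volumes are assumed. Percent change = (sum at Week 24 − sum at index) / sum at index, and only lesion 1 is measured at Week 24.

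| Index volumes | Week 24 volumes | All lesions | Lesion 1 only |
|---|---|---|---|
| 100, 100, 100 | 75, 130, 100 | (305 − 300)/300 = +1.7%; lesion 2 is +30%: non-responder | −25%, no growth seen: both criteria pass |
| 20, 100, 100 | 15, 110, 110 | (235 − 220)/220 = +6.8%: non-responder on the sum | −25%: both criteria pass |
| 100, 100, 100 | 90, 60, 60 | (210 − 300)/300 = −30%: responder | −10%: non-responder |

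The third line shows that error in the sum is not one-sided. In general, if the measured lesions hold a share s of index volume and shrink by exactly 20%, and the unseen ones change by u%, the full change is −20s + u(1 − s). With s = 1/3 this is −6.7% for u = 0 and +6.7% for u = +20.

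**4. What it could do to the rate.** The number k of responders with incomplete target-lesion data is not in the documents. Assume 1 to 5, starting from the 40% row of Table 6-2 (20/50, 95% CI 26.4–54.8%).

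| k | Counted as non-responders, (20 − k)/50 | Counted as missing, (20 − k)/(50 − k) |
|---|---|---|
| 1 | 38.0% (24.7–52.8) | 38.8% (25.2–53.8) |
| 2 | 36.0% (22.9–50.8) | 37.5% (24.0–52.6) |
| 3 | 34.0% (21.2–48.8) | 36.2% (22.7–51.5) |
| 5 | 30.0% (17.9–44.6) | 33.3% (20.0–49.0) |

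In the middle column each patient costs 1/50 = 2 points, and the denominator is fixed. Relative to that rule, 3.5.2 can therefore only raise the rate or leave it unchanged. The right-hand column removes responders only. If partly measured non-responders also became missing, the rate could rise: removing 3 responders and 5 non-responders gives 17/42 = 40.5%.

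**5. Whether any planned analysis varies this.** A partly measured patient with a computed sum is classed as responder or non-responder, not missing, so neither analysis in SAP 3.5.3 touches that patient. The completeness reporting in 3.5.2 compares patients with and without a Week 24 assessment. It does not count incomplete lesion sets.

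**The case against.** The strongest reply is that the rules fit together. If the MRI rule means that no selected lesion yields a volume, then 3.5.2 covers the remaining cases. The efficacy population already works on an at-least-one-lesion basis (protocol 6.8.1, SAP 3.2). A reader might infer that 3.5.2 contradicts the non-responder rule, but the text supports that only on the *any* reading. Even then the overlap is partial, because the MRI rule needs a scan that was performed, while 3.5.2 also covers lesions that were not imaged. This stands; what remains is an unresolved ambiguity.

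A reader might also infer that every unassessed lesion favors response. The third example in the working shows otherwise for the sum. Only the growth check is one-directional.

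Nor does the rule's absence from the protocol show an improper departure. Protocol 6.9 leaves missing-data methods to the SAP, and the version history is partly redacted, so when the rule was added cannot be established. Restricting non-target progression to lesions "with available information at Week 24 or 6 months (+/- 4 weeks) and new lesions" follows the protocol's own rule in 6.8.1 and 6.9, so it is no inconsistency.

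Two further replies have some weight. SAP 3.5.1 refers to the Independent Central Review Charter, which may define the handling of non-evaluable lesions and is not among the documents. SAP 3.3 has all volumetric measurements listed, so affected patients could be found. A listing, however, neither settles the classification nor shows how the rate responds to it.

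**Conclusion.** The point holds as a gap in the primary endpoint definition. SAP 3.5.2 permits a response without verification of the growth criterion for unmeasured target lesions, its relation to the MRI non-responder rule is not stated, and no planned sensitivity analysis examines it.

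The direction is certain in two respects only: an unmeasured lesion cannot fail the growth check, and the rate under 3.5.2 is never below the rate with partly measured patients counted as non-responders. The net bias against complete measurement cannot be derived from the documents. The size rests on an assumed count: 2 points per reclassified responder at n = 50, or 2 to 10 points for 1 to 5 patients, against a 95% interval about 28 points wide at 40%. The remaining safeguards (non-target progression, new lesions, discontinuation, rescue surgery) still apply. The design stands; the definition and its supporting analyses should be completed.

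**What to change.** 1. In SAP 3.5.1, state whether the MRI non-responder rule means any or all of the selected target lesions, and cross-refer to 3.5.2. Distinguish a lesion that was not imaged from one that was imaged but non-evaluable.
2. State there whether the growth criterion counts as met, failed or unknown for an unmeasured lesion, and what response status follows.
3. In SAP 3.5.3, add one sensitivity analysis that counts as a non-responder every patient with any selected target lesion unmeasured at Week 24.
4. Report the number of responders with incompletely measured target lesions.

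The cost is a few sentences, one extra table row and one count, all from data already collected. The supporting estimate may come out lower than the primary one.

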3.5.3 Sensitivity and supportive/supplemental analyses

Supportive analyses reported in this section are targeted to investigate the robustness of the primary analysis, to model assumptions and data limitations using the efficacy population.

Sensitivity Analysis 1

Clinical practice, including frequency of monitoring patients with PROS is highly variable, and it is anticipated that imaging data may not be available at every key time point during the study period. Based on site feasibility discussions, the variability in frequency of imaging are due to the following reasons: individualized monitoring based on patient-specific needs or age; that

imaging may not be necessary/useful to monitor patient response; institution and insurance policies may not allow for frequent imaging.

Therefore a sensitivity analysis will be performed where missing volumetric assessments at week 24 will be multiply imputed for patients with missing response.

Multiple imputation (MI) is a simulation-based approach where missing values are replaced from the conditional distribution of missing data given the observed data and covariates, creating multiple completed data sets. These complete data sets can then be analyzed using standard methods and software for balanced data. Rubin (1987) presented rules how to combine the multiple sets of estimates to produce overall estimates and confidence intervals that adequately incorporate missing data uncertainty. Missing values for the change from index date in the sum of measurable target lesion volume will be imputed simultaneously based on an underlying joint normal distribution. The imputation model will include the longitudinal volumetric measurements (i.e. the MRI scans at index date and at other available time points), as well as covariates such as age, country and PROS lesion type. The number of imputations will be set to 100, the seed for the random function will be set to 45712002 (457<studycode>).

For each patient, the response status will be determined and for each imputed data set the proportion of patients with response will be calculated. The proportions of patients with response for each imputed data set will then be combined into an overall estimate using Rubin's rules (Little and Rubin 2002). The SAS procedures MI and MIANALYZE will be used to generate the multiple imputed data sets and to combine the results, respectively.

Sensitivity Analysis 2

The following sensitivity analyses for the primary endpoint will be performed by imputing best and worst case as outlined below:

- Patients with missing response (definition in [section 3.5.1](#)) at 24 weeks or 6 months (+/- 4 weeks) will be considered as “responder”.
- Patients with missing response (definition in [section 3.5.1](#)) at 24 weeks or 6 months (+/- 4 weeks) will be considered as “non-responder”.

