## **6.9 Handling of missing data**

As this is a retrospective non-interventional study, information may not be systematically collected, resulting in some missing data. Methods of handling missing data for each of the study variables will be detailed in the SAP.

Imaging scans for all measurable lesions may not be available for all patients on the index date. In such cases, the most recent imaging scan conducted during the 12 weeks prior to the index date will be considered as the imaging scan performed on the index date for these patients. This 12 -week window is being utilized based on feasibility assessment of the likelihood of imaging being available at index date and a reasonable time period in which to review imaging data in the pre-index period.

All data available for each patient and each variable will be collected during the pre-index and the study period; appropriate key time-points and associated time windows for the study period (Table 6-1) will be used to analyze the secondary endpoints given there is no common assessment schedule in clinical practice. The number of patients with missing values will be reported.

For the primary analysis, all patients in the efficacy population without missing response will be used (complete case analysis).

Supportive analyses will be performed to investigate the robustness of the primary analysis using the full efficacy population. In particular, a sensitivity analysis will be performed where missing volumetric assessments at Week 24 will be multiply imputed based on a missing at random (MAR) assumption for patients with missing response. The imputation model will include the longitudinal volumetric measurements (i.e. the MRI scans at index date and at Week 48), the measurement at index date, as well as covariates such as age. Additional details will be provided in the SAP.

No imputation will be performed for the non-target lesions, only lesions that have data at index date (or up to 12 weeks prior) and at weeks 24 (+/- 4 weeks) will be used to define progression.

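### The multiple-imputation check models only the summed target-volume change, on an untransformed normal scale, so it does not test the same endpoint as the primary analysis

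*SAP*

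**What the plan says.** SAP 3.5.3 applies multiple imputation to patients with a missing response. It says "Missing values for the change from index date in the sum of measurable target lesion volume will be imputed simultaneously", and that this is "based on an underlying joint normal distribution". The model uses the index scan, scans at other time points, and covariates such as age, country and lesion type. No transform or lower bound is given. After imputation, "For each patient, the response status will be determined and for each imputed data set the proportion of patients with response will be calculated".

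SAP 3.5.1 sets six conditions for response:
- a fall of at least 20% in the sum;
- a condition on single lesions, beginning "None of the individual target lesions has", with a 20% growth limit;
- no permanent discontinuation before 24 weeks;
- no rescue surgery before 24 weeks;
- no non-target progression;
- no new lesion.

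Protocol 6.9 adds: "No imputation will be performed for the non-target lesions". The primary analysis is complete case. Sensitivity Analysis 2 sets all missing responses first to responder and then to non-responder.

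**The concern.** A sensitivity analysis for missing data should estimate the same quantity as the primary analysis under a different assumption about the missing values. Here the imputation supplies one of six response conditions, and three of the others may have no data behind them. If the programmer lets them default to passed, imputed patients face an easier endpoint than observed patients.

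The scale is a second problem. Absolute volume change spreads more widely in patients with large lesions. One normal model therefore gives small lesions changes typical of large ones, including falls of more than the whole index volume.

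At stake is the only model-based check on the complete-case result. Its agreement or disagreement with the primary analysis could come from these two features and say little about the missing data.

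**Working it through.** **1. The plan's own figure.** Protocol Table 6-2 gives exact 95% limits at n = 50. Clopper-Pearson limits are the 0.025 quantile of Beta(x, n-x+1) and the 0.975 quantile of Beta(x+1, n-x). With x = 10, 15, 20 and 25 they give 0.100-0.337, 0.179-0.446, 0.264-0.548 and 0.355-0.645, matching the table. The documents give no figure for the imputation analysis.

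**2. Which conditions can an imputed patient fail?** Under SAP 3.5.1, an MRI done at Week 24 that cannot be measured counts as non-response. A patient who reaches imputation therefore generally has no usable Week 24 MRI.

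| Condition | Status for an imputed patient |
|---|---|
| Sum down at least 20% | Imputed |
| No discontinuation before 24 weeks | Met, by the definition of missing response |
| No rescue surgery before 24 weeks | Met, by the same definition |
| No target lesion up 20% or more | Follows from the sum with one lesion; undetermined with two or three |
| No non-target progression | Read centrally, only from lesions with Week 24 data; not imputed |
| No new lesion | Read centrally from images; not imputed |

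The fourth row in algebra: let one lesion hold share w of the index sum, and let r1 and r2 be the Week 24 to index volume ratios. A responding sum needs w·r1 + (1-w)·r2 ≤ 0.8. With r2 = 1.2 and r1 ≥ 0, this is possible whenever 1.2(1-w) ≤ 0.8, that is, w ≥ 1/3. The imputed sum cannot rule out a growing lesion.

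**3. Simulation inputs.** From the protocol: n = 50 (section 6.6). Assumed, because the documents give no values:
- 30% of responses missing completely at random;
- lognormal index volumes with log-SD 0.5, 1.0 or 1.5;
- log volume ratio with SD 0.25 and mean 0, -0.15, -0.30 or -0.50;
- a share q of volume responders (0, 10% or 20%) failing one of the three open conditions.

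The model drew absolute change given index volume. There were 300 data sets per setting and 20 imputations each (the SAP plans 100). Other scans and covariates were left out. The true volume response is Φ((ln 0.8 - mean)/0.25), with ln 0.8 = -0.223: about 19%, 38%, 62% and 87% for the four means.

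**4. Open conditions taken as passed.** The shift in the overall rate is m·q·p, where m is the missing share and p the volume response among imputed patients. With log-SD 1.0, mean -0.30 and q = 20%, p = 0.555, so 0.30 × 0.20 × 0.555 = 3.3 points; the simulation gave 51.3 - 48.0 = 3.3. Across settings the shift was +0.7 to +2.5 points at q = 10% and +1.4 to +4.7 at q = 20%. It is never negative.

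**5. Scale alone (q = 0).** The shift is m × (imputed minus true response among the missing). With log-SD 1.5 and mean -0.50: 0.30 × (0.669 - 0.873) = -6.1, against -6.0 simulated.

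| True rate | Shift in overall rate (points) |
|---|---|
| about 19% | +1.6 to +5.0 |
| about 38% | -0.4 to +1.4 |
| about 62% | -1.4 to -2.2 |
| about 87% | -1.7 to -6.0 |

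Imputed volumes below zero made up about 2%, 9-10% and 18% of draws at log-SD 0.5, 1.0 and 1.5.

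**6. Both effects, and the repair.** The repaired version imputes the log ratio and applies the open conditions to imputed patients.

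| log-SD, mean, q | True | As planned, open conditions passed | Scale effect | Criteria effect | Net | Repaired |
|---|---|---|---|---|---|---|
| 1.5, 0, 20% | 14.6% | 20.7% | +4.0 | +2.1 | +6.1 | 15.0% |
| 1.0, -0.30, 20% | 49.2% | 51.3% | -1.2 | +3.3 | +2.1 | 49.4% |
| 1.5, -0.50, 10% | 77.9% | 74.9% | -5.0 | +2.0 | -3.0 | 77.6% |

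The net range is -3.0 to +6.1 points at q = 10-20%, and -6.0 to +6.1 when q = 0 is included. The repaired version stayed within about 0.8 points of the truth in every setting. A separate simulation, also with n = 50 and 30% missing, gave -5.5 to +5.6 points, and within about 1 point after repair.

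**The case against.** The strongest reply is that this is a gap in wording. The SAP says response status will be determined for each patient and nowhere waives a condition. It also never writes the word absolute. SAP 3.6 names change and percent change as separate quantities, which makes absolute the natural reading, but no more. If percent change was meant, the scale problem nearly vanishes: with q = 0, the shifts at log-SD 1.0 and 1.5 were -1.5 to +0.6 points, with at most 0.1% of volumes negative. The simulated model is also thinner than the planned one. Adding one further scan (assumed log-ratio correlation 0.8) cut negative draws from about 3%, 11% and 20% to 1%, 7% and 15%. All of this stands and limits the size of the scale effect. It does not supply data on the open conditions.

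Stronger readings are tempting, and the documents do not support them:
- **That the analysis overstates response.** This holds for the open conditions only. The scale effect reverses when true response is high.
- **That imputed patients escape every other condition.** Discontinuation and rescue surgery are settled by the definition of missing response. Rescue surgery covers worsening or new lesions that need intervention, so some severe progression is already non-response.
- **That negative volumes add responders.** A negative draw set to zero is still a 100% fall. Negative draws are a sign of the wrong scale.
- **That the primary result is biased.** It uses no imputation, and Sensitivity Analysis 2 bounds it without a model.

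A few points is also small beside the planned interval widths of 23.7 to 28.9 points. But with 30% missing the best- and worst-case bounds lie 30 points apart, so readers will look to the imputation for something sharper.

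**Conclusion.** The concern holds in this form. As written, Sensitivity Analysis 1 imputes one component of the response definition. For most imputed patients the non-target and new-lesion conditions have no data or rule, and with two or three target lesions neither does the individual-lesion condition. If these are taken as passed, the error from that source is upward or zero. Under the absolute-change reading, the untransformed normal model adds an error that is upward at low true response and downward at high. The net error can go either way, by a few points overall.

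That size rests on n = 50, 30% missing, the assumed spread of volumes and the assumed share failing an open condition; none but n comes from the documents. The gap itself is well established, and the net sign is not. It should be corrected, but it does not touch the primary estimate.

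**What to change.** Amend SAP 3.5.3 in two places.

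1. **Scale.** Impute the log of Week 24 volume over index volume, for the sum or per target lesion, with a small stated offset in case a lesion resolves fully.
2. **Remaining conditions.** Impute a binary indicator for failing the individual-lesion, non-target or new-lesion condition, and count an imputed patient as a responder only if the volume falls by at least 20% and the indicator is clear. Alternatively, impute the composite binary response directly, which settles both points.

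The cost is SAP wording and a few more lines of code. An indicator model may be unstable at this sample size if few patients fail those conditions, and imputing the composite response is then simpler. The sensitivity estimate may come out less favourable. Pooling on the logit scale and dropping country from the model are optional preferences, and the point does not depend on them.
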